## **11.0 Data Management:**

Paper consent will be stored in a locked cabinet in the PT department. All data management will be conducted using the Redcap platform developed and housed at MUSC. All other collected data will be stored electronically in the MUSC OCIO approved secure SharePoint system. Access to this database will be restricted based on netID permissions to a secured server and will only be accessible to IRB study personnel. Identifying information will be removed from the primary database. Identifying information will be stored in a separate file with a unique identifier assigned to the patient to link the two datasets.

Since this study includes only the addition of one physical therapy session a day at an

increased intensity to patients post stroke for 150 patients, it is a rather low risk study. Therefore, our data and safety monitoring plan will be continuous, close monitoring by the study investigator/co-investigators of all participants. The PI and Co-I's will meet every 25 patients to discuss data and safety monitoring. During these meetings we will look for any negative trends in the data we have collected (vitals, NIH stroke scale- ie stroke severity, and functional mobility scores) that could indicate adverse events and provide a timely summary report of adverse events to the IRB/NIH.

Any reportable safety events that are unexpected, serious or may be related to the subjects' participation in this research will be reported to the MUSC IRB in accordance with their policies.

Once the Principal Investigator (PI) determines that an adverse event meets the IRBs' reporting requirements, she will report the SAE, and related safety information, to the IRB. Supporting documents, including a copy of the Informed Consent (IC), will also be attached. For reasons of confidentiality, subjects' names will not be included in the report. If the adverse event results in the need to revise the informed consent, or other study documents, the PI will submit a study amendment to the IRB. Any trend in a type of adverse event will be relayed to the IRB as soon as the trend is noted. All events that do not meet the criteria of significant or trending, will be recorded in a summary form and included at the close of the study. Per consistency with the NIH guidelines- all serious and significant adverse events involving risks to a participant or suspension/termination of IRB approval for this study will be immediately reported to the sponsor.

For the primary outcome, PASS, to test the null hypothesis of no difference between the group versus a MCID of 2.7, at 5% significance level, using a repeated measure designs at 4 time points and an autoregressive correlation of .6, and a standard deviation of 720 with more than 80% power. Although there is power to detect a moderately small difference (2.7 as mentioned), the purpose here is also to estimate the difference between the two randomized groups. Based on the past literature, in similar populations the standard deviation of PASS measurements is at the most 7.20 Using this, with a sample of 75 patients in each group, with 95% confidence at the end of the study we can estimate this difference within a margin of error of 2.3.

We are planning to conduct the analysis using intention to treat paradigm. In a preliminary analysis we will compute all summary statistics. Initial plots, such as spaghetti plots, will be used to guide our analyses. A general linear mixed model approach will be used to analyze all the outcomes. This model will account for the correlations between time points using either a compound symmetric or spatial structure for the covariance matrix. Post-hoc analyses using Tukey type adjustments will be performed to obtain least squares estimates of the differences between the two randomized groups. Although the study is powered based on only the primary outcome (PASS), we will apply multiple comparisons adjustments for the rest of the outcomes, using Bonferroni corrections. We will test for the assumptions using diagnostic procedures and take appropriate actions if needed. Also, we will define an outcome to be 'favorable' or 'unfavorable' based on a threshold and apply generalized linear mixed models with logistic link and repeat the analyses. We will attempt to minimize drop- outs but in case of missing data, we will assume Missing at Random or Missing Completely at Random. If necessary we will perform multiple imputations. For all analyses, we will use SAS, (MIXED, GLIMMIX, MI and MIANALYZE).

The RESTORE registry (Pro#00037803), from which this study will recruit subjects, also serves as a data analysis tool by which interdisciplinary teams may share data across projects and provide MUSC's stroke recovery research community with a more complete registry with key stroke elements. Some subjects may have participated or will participate in other stroke related research studies at MUSC. Sharing data from this and other stroke research studies with RESTORE will allow for more targeted recruitment efforts in the future and could reduce the burden placed on subjects by reducing the duplicative efforts of collecting common data and physical function assessments requested by multiple studies and storing them in one centralized and secure location. The third Aim of this study leverages this ability, as other studies will be better able to target their recruitment based on the information collected in these assessments.

Subjects are informed in the consent process if they enroll into the RESTORE registry, their data from this study will be shared. Subjects will be asked to sign a HIPAA authorization stating their health information may be disclosed to MUSC investigators requiring their data for their research projects upon approval by an Institutional Review Board.

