## **10.0 Study Design:**

This study will be designed as a randomized control trial with a 1:1 randomization. This study will utilize a permuted block design to randomly allocate a participant to a treatment group, while maintaining a balance across treatment groups. All patients will be identified and consented within 24 hours of admission.

The treatment group will receive increased frequency of PT services within the first 3-5 days of admission, followed by daily PT services for the duration of their inpatient stay. As part of the increased intensity of the treatment provided- this group will receive error augmentation training where the treating therapist will induce errors throughout mobility to challenge the patients rather than facilitating error-free movement. The deficits identified on evaluation will be targeted and emphasized throughout all therapy sessions. For patients with hemiparesis, the hemiparetic limb will be resisted during mobility. For patients with balance impairments- balance will be challenged by narrowing the base of support and resisting midline positioning

toward the side of the balance impairment. The treatment as usual group will receive standard care of PT services 3-5 times per week during their hospitalization which focuses on performing bed mobility, transfers and ambulation vs wheelchair mobility as able. Safety will be ensured throughout therapy sessions. Fall risk will be avoided with the use of a gait belt and non-skid socks and cerebral perfusion concerns will be mitigated by checking a resting blood pressure prior to upright mobility. The Postural Assessment Stroke Scale will be obtained as part of the initial PT clinical evaluation, on day three of hospital admission and at 90 day follow up. Follow up will be conducted (at 90 days +/- 15 days) via neurology clinic- either in person, through virtual clinic or, patient will be contacted via password protected Zoom. NIHSS and MRS scores will also be obtained from patient's chart on admission and at 90 day follow up. All of this data will be collected prospectively for both groups for this research study.

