Precaution will be taken to lessen the probability of risks; despite increased frequency of treatments, duration of upright will still be approached cautiously within the first 24 hours s/p stroke for cerebral perfusion. ALL stroke patients will be returned to supine within 24 hours post stroke and maintain head of bed <30 degrees except for medication, meals, and therapy. Therapy will be stopped if patient deemed medically unstable for increased frequency of treatments by the Stroke NP, Attendings, Fellow, or PI; this decision will be documented via "bed rest" orders in the patient's electronic medical chart, so that the study team is aware to avoid progressive frequent upright mobilization.

**Data collection:** Patient data will be collected from their medical record. Data collected from EPIC/patient's MUSC EMR will be coded in the research database. Data collected include:

- 1) Demographics: sex, age, race
- 2) Stroke risk factors: history of HTN, HLD, A-fib, or DM
- 3) Stroke specifics: type of stroke (hemorrhagic vs ischemic), location of stroke, stroke severity (measured by NIHSS & MRS), time of symptoms to presentation, intervention (tPA or thrombectomy) and complications
- 3) Physical Performance and Functional Measures: Postural assessment stroke scale scores on evaluation, day three and 90 day follow up. Discharge disposition recommended vs ultimate discharge disposition, hospital length of stay.

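### The safety meetings are to look for NIHSS trends, but no NIHSS is scheduled between the first therapy session and discharge, so this stream could miss or delay signs of in-hospital neurological worsening

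*Combined protocol and SAP*

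**What the plan says.** Section 11.0 (Data Management) holds the data and safety monitoring plan. It describes continuous monitoring by the investigators and a meeting every 25 patients, at which "we will look for any negative trends in the data we have collected (vitals, NIH stroke scale- ie stroke severity, and functional mobility scores").

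Section 10.0 (Study Design) gives the only timing for the NIHSS: "NIHSS and MRS scores will also be obtained from patient's chart on admission and at 90 day follow up". The window is stated nearby: "Follow up will be conducted (at 90 days +/- 15 days) via neurology clinic". The data collection list in the same section names "stroke severity (measured by NIHSS & MRS), time of symptoms to presentation, intervention (tPA or thrombectomy) and complications" and adds no further NIHSS time point.

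The intervention is concentrated early: "The treatment group will receive increased frequency of PT services within the first 3-5 days of admission", with daily sessions for the rest of the stay. On entry, "All patients will be identified and consented within 24 hours of admission", and Section 5.0 places randomisation after consent.

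**The concern.** The NIHSS is the measure that Section 11.0 itself equates with stroke severity, and the meetings are meant to find trends in it that could indicate adverse events. A trend within a patient needs a second value, and the second value is scheduled about three months after the stay in which the intervention is given.

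This matters because of the harm in question. Section 13.0 lists worsening weakness and worsening stroke among the risks of early mobilisation. Section 3.0 cites the concern from an earlier trial of very early mobilisation that it may worsen stroke outcomes. Aim 3 is to ensure that the higher dose is safe. The experimental arm receives more sessions, made deliberately harder by error augmentation. If those sessions caused neurological decline in hospital, the stream most directly tied to that harm would hold no scheduled observation from the relevant period.

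**Working it through.** No sample size, power or error rate is involved, so there is no figure in the plan to reproduce. The check compares what the meetings are to review with what is scheduled.

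**1. NIHSS values per patient.** Scheduled in Section 10.0: admission and 90-day follow-up, so 2. Between the first session and discharge: 0 of 2.

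**2. When the second value arrives.** 90 − 15 = 75 and 90 + 15 = 105, so day 75 to 105.

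**3. What two values can show.** Write N0 for the admission score, Nh for the unscheduled score in hospital and N90 for the follow-up score, with higher meaning worse. The recorded change is N90 − N0.
- Worsening that later recovers: Nh > N0 but N90 ≤ N0. The recorded change is zero or negative, so the patient appears stable or improved.
- Lasting worsening: Nh > N0 and N90 > N0. The recorded change is positive, but it is seen only from day 75. It cannot be told apart from an event after discharge.
- Withdrawn for worsening: Section 12.0 removes patients for worsening medical status, for instability that limits mobility, or for ICU transfer. N90 may then be absent, leaving N0 alone.

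**4. What a meeting would hold.** At full enrolment there are 150 / 25 = 6 meetings. At any of them, a patient whose day 75 has not been reached has only the admission NIHSS. The accrual rate is not given, so the share of such patients cannot be computed.

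**5. The other in-hospital signals.**

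| Signal | Where |
|---|---|
| PASS and AMPAC at day three and discharge | Section 4.0; Hypothesis 2 in Section 1.0 also uses change from admission to discharge |
| Adverse events in chart and research record | Section 7.0 |
| Complications; bed rest orders that stop therapy | Section 10.0 |
| Continuous monitoring by the investigators | Section 11.0 |
| Withdrawal for worsening or ICU transfer | Section 12.0 |

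On mobility scores, the Section 10.0 list gives "Postural assessment stroke scale scores on evaluation, day three and 90 day follow up", with no discharge value. Section 11.0, however, plans the PASS analysis on 4 time points. That matches Section 4.0 (evaluation, day three, discharge, 90 days) and not the three in Section 10.0. The better-supported count of in-hospital mobility assessments after baseline is therefore 2.

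**The case against.** The strongest reply is that a meeting every 25 patients is an aggregate check and was never the means of catching an individual who deteriorates. That task falls to continuous clinical monitoring, adverse event records, bed rest orders, immediate reporting of serious events, and withdrawal. Every participant has motor involvement under Section 5.0, so PASS and AMPAC at day three and discharge would register much motor decline. Withdrawals for worsening are countable events in the exposure period itself. The NIHSS is not an endpoint in Section 4.0, and routine care may chart it more often than the research schedule asks.

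Most of this stands, and it limits the point to one stream. It does not remove the mismatch. The NIHSS timing is stated explicitly, so the gap is not just unwritten detail, and the plan does not arrange to collect any further values that routine care may chart. PASS measures postural control, so it is a relevant but incomplete proxy for neurological status.

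A reader might also infer that vitals are reviewed but never collected, since the Section 10.0 data list omits them. The document does not support that. Section 11.0 counts vitals among data already collected, and blood pressure is taken before sessions ("cerebral perfusion concerns will be mitigated by checking a resting blood pressure prior to upright mobility"; also Section 13.0). The list is worded as open, and it also leaves out AMPAC and 30-day readmission, both named in Section 4.0. Absence from that list shows little.

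**Conclusion.** The point holds for the NIHSS stream. A plan followed exactly schedules no NIHSS between the first session and discharge. The stream could miss in-hospital worsening that later recovers, would show lasting worsening only at day 75 to 105 without dating it to the stay, and may lose the patients withdrawn for worsening.

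Two stronger readings are tempting. One is that the trial has no means of seeing neurological harm in hospital; the signals tabulated above contradict this. The other is that the NIHSS as scheduled cannot show worsening at all; a lasting decline could still appear at follow-up, although late.

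The gap is minor to moderate. The number of events missed cannot be estimated, because the document gives neither length of stay nor a rate of early deterioration. The conclusion assumes that the NIHSS timing in Section 10.0 is complete and that the 90-day window is counted from about the time of the stroke or admission.

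**What to change.** In both arms, abstract from the chart, as far as consent allows:
- the last NIHSS before randomisation;
- the NIHSS nearest day three;
- the NIHSS nearest discharge;
- the NIHSS nearest any withdrawal for worsening status or ICU transfer.

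Use the last pre-randomisation value as the reference. Consent may come up to 24 hours after admission, so the admission score may predate tPA or thrombectomy. Add these time points to the Section 10.0 schedule and data list. At each 25-patient meeting, review change from the reference value by arm, with the number missing, alongside counts of withdrawals for worsening. Thresholds and actions stay with the clinical team.

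The cost is a short amendment, a few REDCap fields and some chart abstraction per patient; no new patient assessment is needed. The downside is that charted values will be incomplete and may be recorded more often in patients who worsen. Reporting the number missing makes this visible but does not correct it, so the trend should be read as a safety screen and not as an unbiased comparison between arms.

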### Aims & Hypotheses:

**Aim 1:** To determine the impact of increased frequency and intensity of PT services compared to the usual care PT on discharge disposition of patients post-stroke.

**Hypothesis 1:** We hypothesize that patients receiving an increased frequency of PT services will have higher rate of discharging to home/acute rehabilitation center than to a subacute rehabilitation/skilled nursing facility compared to patients in the usual care PT group.

**Aim 2:** To determine the impact of increased frequency and intensity of PT services, as opposed to usual care, on functional mobility.

**Hypothesis 2:** We hypothesize that patients in the treatment physical therapy group will demonstrate higher degree of improvement on the Activity Measure for Post Acute Care (AMPAC) and Postural Assessment Stroke Scale (PASS) from admission to time of discharge from the hospital and at 90-day follow up. We also expect lower overall Modified Rankin Scale (mRS) scores for the increased frequency PT group compared the usual care PT group at three months post stroke.

**Aim 3:** To ensure that high frequency dosage is safe and feasible to implement the proposed PT regimen in the acute inpatient setting.

**Hypothesis 3:** We hypothesize that there will be fewer adverse events experienced by patients in the increased frequency compared to the usual care group.

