#### **4.0 Study Endpoints**

Physical Performance and Functional Measures: PASS scores & AMPAC scores on evaluation, day three, discharge, and 90 day follow up. Discharge disposition recommended vs ultimate discharge disposition, hospital length of stay, and 30-day readmission.

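### The stated power for PASS fits an average over visits, not Hypothesis 2's discharge and 90-day contrasts, and the margin of error beside it is that of a single visit

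*Combined protocol and SAP*

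**What the plan says.** Section 11.0 makes PASS the primary outcome and the only one on which the study is powered. The test is described as "to test the null hypothesis of no difference between the group versus a MCID of 2.7", at the 5% level, using "repeated measure designs at 4 time points and an autoregressive correlation of .6, and a standard deviation of 720 with more than 80% power". No visit, average, change score or baseline adjustment is named. The same paragraph gives a 95% margin of error of 2.3 points with 75 patients per group, as does Section 6.0.

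The analysis is a mixed model "using either a compound symmetric or spatial structure for the covariance matrix". Group differences come from Tukey-adjusted post-hoc comparisons, and "Initial plots, such as spaghetti plots, will be used to guide our analyses".

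Hypothesis 2 (Aims & Hypotheses) concerns greater improvement in PASS "from admission to time of discharge from the hospital and at 90-day follow up".

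The visit lists differ. Section 4.0 has "PASS scores & AMPAC scores on evaluation, day three, discharge, and 90 day follow up". Section 10.0 has PASS at "initial PT clinical evaluation, on day three of hospital admission and at 90 day follow up", and its data-collection list has "Postural assessment stroke scale scores on evaluation, day three and 90 day follow up". Neither list in Section 10.0 includes discharge.

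**The concern.** A power figure belongs to one contrast. Here the power sentence, the margin of error and Hypothesis 2 seem to refer to three different ones: a group difference over four visits, a difference at one visit, and improvement from admission to two particular visits. Their variances differ widely, so one sample size gives very different power for each.

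The four-visit reading has a further problem. The first listed visit is the evaluation before treatment, where randomised groups should not differ. Counting it as an outcome in the group effect dilutes any treatment difference.

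At stake is how the primary result is read. If a discharge or 90-day comparison is taken as primary and correlation decays as the planning value implies, a null result is weaker evidence against 2.7 points than the stated power suggests.

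**Working it through.** **Inputs.** Difference 2.7 points, 5% level, 4 time points and AR correlation 0.6 (Section 11.0); 75 per arm (Sections 6.0 and 11.0); 1:1 allocation (Section 10.0). The SD is taken as 7, because Section 6.0 prints the 20 after it as a reference mark. The printed 720 is treated as the same figure, and 7.2 is run as the other possible reading. Assumptions: two-sided test (sidedness is not stated), no loss (no rate is given), and AR decay in equal steps in the order evaluation, day three, discharge, 90 days.

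**Formula.** SE of a single-visit difference = 7 × √(2/75) = 1.143. For a contrast whose variance is v times that of a single visit, power = Φ(effect / (1.143 × √v) − 1.96).

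**Step 1: reproduce the plan's power under AR 0.6.**
- Four-visit mean: v = [4 + 2(3×0.6 + 2×0.36 + 0.216)]/16 = 0.592. Power = Φ(2.7/0.880 − 1.96) = 86.6% (84.7% at SD 7.2).
- Mean of three post-baseline visits: v = [3 + 2(2×0.6 + 0.36)]/9 = 0.680, power 82% (79.5% at SD 7.2).
- The same mean adjusted for admission PASS: v = 0.680 − 0.392² = 0.526, power 90%.

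**Step 2: the evaluation visit.** With effects 0, 2.7, 2.7 and 2.7, the four-visit mean difference is 8.1/4 = 2.025. Power = Φ(2.025/0.880 − 1.96) = 63%. Under compound symmetry 0.6, v = (4 + 12×0.6)/16 = 0.70 and power is 56%, against 81% with the full effect at all four visits.

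**Step 3: Hypothesis 2's contrasts.** For a change score v = 2(1 − r). For a baseline-adjusted comparison v = 1 − r². Here r is the correlation with admission PASS.

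| Contrast | r (AR) | v | Power, AR 0.6 | Power, compound symmetry 0.6 |
|---|---|---|---|---|
| Change to discharge | 0.36 | 1.280 | 55% | 75% (v = 0.80) |
| Change to 90 days | 0.216 | 1.568 | 47% | 75% (v = 0.80) |
| Adjusted, discharge | 0.36 | 0.870 | 72% | 84% (v = 0.64) |
| Adjusted, 90 days | 0.216 | 0.953 | 68% | 84% (v = 0.64) |

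Break-even: 80% power at 2.7 points needs v ≤ (2.7/(2.8016 × 1.143))² = 0.711. That means r of at least about 0.54 (adjusted) or 0.64 (change).

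**Step 4: the margin.** 1.96 × 1.143 = 2.24 (2.30 at SD 7.2), which matches the stated 2.3. A four-visit mean under AR 0.6 would give 2.24 × √0.592 = 1.72. The power of a single-visit difference is Φ(2.7/1.143 − 1.96) = 65.6% (63% at SD 7.2).

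**Sensitivity.**
- At SD 7.2 the adjusted discharge and 90-day figures under AR 0.6 are 69% and 65%.
- A one-sided 5% test under AR 0.6 gives 67% and 60% for the change scores. The adjusted comparisons have Φ(2.532 − 1.645) = 81% at discharge and Φ(2.419 − 1.645) = 78% at 90 days.
- With Section 10.0's three visits, the 90-day correlation becomes 0.36, giving 55% (change) and 72% (adjusted).

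**The case against.** The strongest reply is that the ordinary reading of Section 11.0 is a group difference across the four visits, and that this reading does exceed 80% (86.6% at SD 7; 81% under compound symmetry). That stands: the figure is not an arithmetic error. What it leaves open is that this average requires the full 2.7 points at a visit before treatment.

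A second reply is that the Hypothesis 2 shortfall rests on AR decay by visit order, a spacing the plan does not define. That also stands. A reader might infer that the trial is underpowered for discharge and 90 days, but the documents do not establish this: with baseline adjustment and compound symmetry, power is 84%. The uncertainty also runs the other way. If correlation decayed with calendar time, the admission-to-90-day correlation would approach zero and adjusted power would be at most about 66%.

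Three other stronger readings go too far.
- That the sponsor's calculation did average in the evaluation visit: the method is not shown, so the 63% is conditional.
- That no single-visit comparison reaches 80% under AR 0.6: baseline-adjusted day-three PASS has r = 0.6, v = 0.64 and 84%. Day three is not a time named in Hypothesis 2.
- That the contrast will be picked from the plots: the plan says only that plots guide the analyses. The fair criticism is that nothing fixes the contrast beforehand.

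Finally, the plan also aims to estimate the difference, and an interval would show its own imprecision. True, but the interval does not say which contrast was intended.

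**Conclusion.** The concern holds as a mismatch between the stated power and the contrasts of interest, and it should be fixed. The claim of more than 80% is met by averages over visits that the plan does not name. The four-visit average falls to 63% (56% under compound symmetry) if there is no group difference at the pre-treatment evaluation. For Hypothesis 2, power is 47% to 72% under AR 0.6 by visit order and 75% to 84% under compound symmetry, so the size of that shortfall depends on the correlation pattern. The power and the 2.3 margin appear to describe different contrasts, since the margin is a single-visit figure with 65.6% power.

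These figures assume SD 7, 75 analysed per arm and a two-sided 5% test. They include no loss and no Tukey adjustment, either of which would lower power.

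**What to change.** 1. Before data are examined, name one primary PASS contrast. Adjust it for admission PASS, which is already collected, and do not count the admission visit as an outcome in the group effect.
2. Restate power and margin of error for that same contrast, with the assumed correlation pattern. For example, baseline-adjusted 90-day PASS has about 68% power at 2.7 points under AR 0.6, reaching 80% at 2.8016 × 1.143 × √0.953 ≈ 3.1 points, with a margin of 2.24 × √0.953 ≈ 2.19. Under compound symmetry 0.6 it has 84% at 2.7 points and a margin of 2.24 × 0.8 ≈ 1.79. The choice of contrast is the sponsor's.
3. Reconcile Section 4.0, which lists a discharge PASS, with Section 10.0, which does not, so that the four time points in Section 11.0 match the schedule.

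The cost is protocol and analysis wording, with no extra patients. The downside is that the stated power or detectable difference may look less favourable.

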### **3.0 Intervention to be studied**

Early mobilization is a widely accepted pillar of acute hospital therapy services. In most populations, early mobility is regarded as safe, feasible, and yields positive results. A considerable amount of clinical and scientific literature has evaluated and upheld the positive effect of early mobility on patient safety, ICU delirium, duration of mechanical ventilation, hospital length of stay, functional mobility, ambulation ability, and mortality. However, most of the research in the field of early mobilization has focused on intensive care patients with multiple medical comorbidities.

The consideration of an acute stroke diagnosis in relation to the approach of acute care PT and “early mobility” is limited. The AVERT trial was novel in opening the doors to considering physical therapy’s approach to acute stroke care on these dedicated stroke units, critical since earlier research surmised that complications of immobility could be estimated to account for as many as 51% of death in the first 30 days post stroke. The results of the AVERT trial, however, raised concern that very early mobilization may cause changes in cerebral blood flow and blood pressure leading to worsened stroke outcomes, increased mortality and increased rate of falls during early mobility.

From the publication of the AVERT trial, there has been a rise in clinical interest regarding the correlation of early mobility and improved functional outcomes post stroke. The majority of physical therapy studies in the acute stroke population have only examined the optimal time to begin mobilization post admission to the hospital. This project proposes the idea that patients with acute stroke may not be able to tolerate an extensive early mobility program.

Instead, patients may benefit from shorter more frequent sessions of therapy early in their recovery to focus on specific areas such as seated postural control, motor recruitment strategies, and transfer training delivered in separate sessions. We hypothesize that the approach of shorter, more frequent sessions of intense quality therapy services will negate the post stroke fatigue factor. Thus, allowing patients to progress functional mobility with improved tolerance to therapy sessions, frequent repetition, as well as implementation of motor learning principles to ensure carryover by providing distributed over massed practice.

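### Discharge disposition (Aim 1) and 30-day readmission fall under a repeated-measures linear model that reduces to an unadjusted regression on a category, forgoing admission NIHSS and leaving deaths unclassified

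*Combined protocol and SAP*

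**What the plan says.** The statistical text stands in section 11.0 (Data Management). Its general rule is "A general linear mixed model approach will be used to analyze all the outcomes". It continues "This model will account for the correlations between time points", offers two covariance structures for this, and reports least squares differences between the arms. A second analysis is then added: "we will define an outcome to be 'favorable' or 'unfavorable' based on a threshold", after which the team will "apply generalized linear mixed models with logistic link and repeat the analyses". The outcome, threshold and visit for that second analysis are not given. PASS is the primary and only powered outcome. For the others, "we will apply multiple comparisons adjustments for the rest of the outcomes, using Bonferroni corrections". No baseline covariate is named.

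Aim 1 concerns discharge disposition. Hypothesis 1 expects a "higher rate of discharging to home/acute rehabilitation center than to a subacute rehabilitation/skilled nursing facility". Section 4.0 lists "Discharge disposition recommended vs ultimate discharge disposition, hospital length of stay, and 30-day readmission". Neither disposition nor readmission is mentioned by name in the analysis text. Admission NIHSS is collected (section 10.0), and eligibility spans scores of 2 to 18 (section 5.0).

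**The concern.** A model built around correlation between visits has nothing to model when a patient contributes one value. For disposition and readmission the general rule becomes an ordinary linear regression of a coded category on treatment arm. A logistic route exists, but it is an additional repeat and is tied to neither endpoint.

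Three things are then left unsettled or forgone for the first-listed aim:

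- **Precision.** Stroke severity at admission may well predict where a patient is discharged. It is already recorded, yet no adjustment is planned.
- **Classification.** The Hypothesis 1 split covers four destinations and does not place deaths or any other destination. Section 3.0 itself reports that an earlier trial of very early mobilization raised concern about "worsened stroke outcomes, increased mortality and increased rate of falls during early mobility", so the two arms need not have equal numbers in that group.
- **Which disposition.** Both a recommended and an ultimate disposition are collected, and the plan does not say which one tests Hypothesis 1.

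**Working it through.** **The plan's own figures (PASS only).** Margin of error = 1.96 × SD × √(2/75). With SD 7.2 this is 1.96 × 7.2 × 0.1633 = 2.30; with SD 7 it is 2.24. The stated 2.3 is reproduced. For power, the variance factor for the mean of four visits under autoregressive correlation 0.6 is [4 + 2(3×0.6 + 2×0.36 + 0.216)]/16 = 0.592. With SD 7.2 the standard error is 7.2 × √0.592 × 0.1633 = 0.905. Then 2.7/0.905 − 1.96 = 1.02, which gives about 85% power, in line with the stated figure of more than 80%. No figure is given for disposition or readmission, so every rate below is an assumption.

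**Link alone, disposition.** With 75 per arm and favourable rates of 50 v 70, 60 v 80, 70 v 85, 60 v 60 and 70 v 70%, enumerating all possible tables shows the unadjusted linear and Wald-logistic tests disagreeing at 5% in 0 to 0.5% of trials. In simulation, type I error is 4.6–5.9% for the unadjusted linear model and 4.4–5.5% for the NIHSS-adjusted logistic model. The link changes what is reported: 60 v 80% is a risk difference of 20 points or an odds ratio of (0.8/0.2)/(0.6/0.4) = 2.67.

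**Adjustment for NIHSS.** This used 6,000 simulated trials per scenario, with NIHSS on 2–18 either right-skewed (mean 6.7, SD 4.2) or uniform (mean 10, SD 4.9). For 60 v 80% the results were:

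| Assumed odds ratio per NIHSS point | Power, unadjusted linear | Power, adjusted logistic | 95% CI half-width, standardised risk difference (unadjusted 14.4) |
|---|---|---|---|
| 0.95 | 76.8–78.0% | 77.1–78.3% | 14.2 points |
| 0.90 | 76.7–77.2% | 78.4–78.6% | 13.9–14.0 |
| 0.85 | 76.9–77.1% | 80.8–81.8% | 13.5–13.6 |
| 0.80 | 76.2–77.2% | 83.4–84.6% | 13.0–13.1 |

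Over all three pairs of rates, the power change is −1.5 to +0.3 points at 0.95, +0.5 to +1.7 at 0.90, +2.2 to +4.9 at 0.85 and +5.8 to +7.9 at 0.80. If NIHSS is unrelated to disposition it is −1.3 to +0.1. At 0.80 the variance ratio is 0.80–0.87, equivalent to 75/0.87 ≈ 86 up to 75/0.80 ≈ 94 patients per arm. Adjusted linear regression gives nearly the same power, so the gain comes from the covariate and not from the link.

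**Classification of deaths and other destinations (invented counts, to show the mechanism).** Take 45 v 52 favourable of 75.

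- Counted as not favourable: 52/75 − 45/75 = 9.3 points (95% CI −5.9 to 24.6).
- Excluded, 4 v 4 such patients: 52/71 − 45/71 = 9.9.
- Excluded, 2 v 6: 52/69 − 45/73 = 13.7.
- Excluded, 3 v 9: 52/66 − 45/72 = 16.3 (1.4 to 31.2).

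Exclusion moves the estimate little when the arms are balanced. When they are not, it favours the arm with more deaths.

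**Readmission.** At an assumed 10% v 5%, exact enumeration gives power of 21.8% for the linear test, 13.9% for Wald-logistic and 23.1% for the likelihood-ratio test. Linear and Wald disagree in 7.9% of trials. The score test gives 21.8%. With 5% in both arms, the likelihood-ratio test rejects in 7.3% of trials and the score test in 4.9%, so the score test is the safer of the two at low rates.

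**The case against.** The strongest reply is that the plan does assign a model and an effect measure. The general rule covers every outcome, and a least squares difference on 0/1 coding is a risk difference. The logistic analysis comes second, as a repeat, so an order can be read. This stands. A reader might infer that Aim 1 has no analysis at all, or that the linear analysis would be invalid. The documents do not support either reading, and the calculations show type I error broadly held.

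It is also fair to say that an unadjusted randomised comparison is valid, that the documents give no association between NIHSS and disposition, and that the death counts are made up. The mortality concern in section 3.0 comes from earlier work. This trial requires medical stability and returns patients to supine in the first 24 hours. All of this limits how large an effect can be claimed. It does not supply the missing classification.

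Two further replies are weaker. The plan promises to check assumptions and act if needed, and it lists GLIMMIX, so a binary outcome could be moved there. That would be a decision made after looking at the data. Hypothesis 1 does supply a binary split, and its wording suggests actual discharge. Even so, the analysis text does not link the split to a model, and section 4.0 lists both dispositions without choosing.

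**Conclusion.** The concern holds in a limited form. For disposition and readmission the assigned model collapses to an unadjusted linear regression on a coded category, and the logistic repeat is not attached to either endpoint. For disposition the link is close to harmless. The real losses are the precision available from admission NIHSS and a fixed rule for deaths, other destinations and the choice between recommended and ultimate disposition. For readmission the choice of test can matter if events are few.

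The gain from adjustment is roughly 1.5 to 8 power points at odds ratios of 0.90 to 0.80 per NIHSS point, with 0.5 the smallest value seen at 0.90, and nothing or a small loss if the association is weak or absent. These figures assume 75 per arm, two-sided 5% tests, and rates and NIHSS distributions that the documents do not give.

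A reader might infer that the trial's main result is at risk. It is not: PASS is continuous, repeated and separately powered. Nor do the illustrative counts show that deaths will differ between arms here. The change is worth making before the data are analysed because Aim 1 is the first-listed aim and the cost is small.

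**What to change.** - Keep the linear mixed model for PASS and AMPAC.
- Make the deciding Aim 1 analysis a logistic regression of ultimate discharge disposition on the Hypothesis 1 split, adjusted for admission NIHSS, and report a standardised risk difference with 95% CI.
- Count deaths and other destinations as not favourable. This keeps all randomised patients, as the plan's intention-to-treat principle requires. Repeat with those patients excluded as a sensitivity analysis.
- For 30-day readmission, use a binary-outcome analysis with a score or likelihood-ratio test, not a Wald test. Report a risk difference, and state a rule for deaths before day 30.
- Optional: name one cut-point and one visit for any dichotomised PASS analysis and label it supportive; state the scale for length of stay.

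**Cost.** Plan wording, two standard models and one post-estimation step (delta method or bootstrap) for the risk difference. No new data or patients are needed. If NIHSS is unrelated or only weakly related to disposition, adjustment may cost up to about 1.5 power points at 5%, or about 2 at 1% (the level if Bonferroni were applied over an assumed five outcomes).
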